5.3. Administration of Study Drug and Compliance to Regimen

Study Coordinator orders and obtains medication dispensed from the Research Drug Manager (or research pharmacy unit if available). Subjects will self-administer medication and will be instructed to bring back empty or partially empty bottles to each in-person study visit for medication reconciliation and compliance procedures. Subjects will be interviewed by phone every two weeks to ensure compliance with study regimen as well as to note potential AEs.

5.4. Prior and Concomitant Therapy

Exclusionary medications:

Drugs that affect glucose and lipid homeostasis. Anti-diabetes drugs (including but not limited to

HSC 20190766H Version: 2.4 10-29-2020

metformin, sulfonylureas, other SGLT2i, DPP inhibitors, etc). Glucocorticoids (prednisone, methylprednisone, hydrocortisone). Atypical antipsychotics (olanzapine, clozapine, etc). Anti-rejection medications (prograf, cellcept). Anti-retrovirals (protease inhibitors).

Treatment with anticoagulants (warfarin). Aspirin (up to 325 mg) and clopidogrel will be permitted if these can be held for seven days prior to the biopsies.

5.5. Packaging

Nature and Contents of the Container - bottle of 30 tablets

5.6. Handling of Study Drug

Research Drug Manager will be responsible for receipt, storage, dispensing, handling and destruction of Study Drug.

5.6.1. Receipt of Drug Supplies

Any damaged or unusable study drug in a given shipment will be documented by the Research Drug Manager. The Research Drug Manager will notify the Material Sponsor of any damaged study drug.

5.6.2. Storage

The drug product used for clinical studies should be stored at USP recommended room temperature. Excursions from the recommended room temperature will be documented by the Research Drug Manager and acted upon after consultation with Material Sponsor (or AstraZeneca, manufacturer). Expirations on the study product will be honored.

For more details, please see also Farxiga Package Insert or Farxiga Health Care Provider website: https://www.farxiga-hcp.com/

5.6.3. Dispensing of Study Drug

Designated staff from the Research Drug Management unit will maintain the Drug Administration Logs to track how, when and to whom the investigational drug was dispensed and assigned to subjects. Study clinical staff will keep administration records regarding dosing, unused drug, drug damaged, or wasted.

Study drug may be dispensed to participants in person, at home visits, curbside delivery, or by U.S. mail.

Version: 2.4 10-29-2020

Labeling study drug will include FDA required language including "Caution: New Drug--Limited by Federal (or United States) law to investigational use."

Routine Study Drug reconciliation will be performed based on clinical site policy and standard operating procedures.

5.6.4. Return or Destruction of Study Drug

The procedures for final reconciliation of the site's drug supply at the end of the study will be in accordance with local site Drug Management standard operating procedures.

There are no special precautions cited for disposal of dapagliflozin.

6. Study Procedures

6.1. Study visits.

Visits will be performed at the UT Health San Antonio Medical Arts and Research Center (MARC) or at the Barshop Institute Clinical Research Center (BICRC), except for magnetic resonance studies that will be done at the Research Imaging Institute. Participants will arrive fasting (10-12 h) for visits involving lab work, imaging, or biopsies. If the study investigator determines that it is in the greater interest of the safety of the study staff and study participants, the study staff may perform home visits or video telehealth visits. Participants will be given a Fitbit Bluetooth scale to obtain their weight measurement at home. The data will be transmitted to the research staff electronically through the Fitbit app. The study staff will receive the information in an individual, non-identifiable email account that the study staff will create for each study participant. If the participant does not have access to a mobile device or cannot access the Fitbit app, the study staff will collect the data during home visits or by telephone. The scales will be provided to study participants at no charge. Visits that require DXA scans and MRI scans may be performed interchangeably due to availability of the DXA and MRI scanners.

6.1.1. Visit 1 (Day -17 to -21)

Eligible subjects present to the research unit at appointed time for informed consent. Consenting subjects will arrive fasting to undergo vital sign evaluation, medical history, physical exam, safety labs [comprehensive metabolic panel (CMP), complete blood count with differential (CBC), coagulation labs (PT/PTT/INR), HbA1c, TSH, routine urinalysis, lipid panel, insulin and FFA, and the Montreal Cognitive Assessment (participants must score ≥21 to be eligible). Visit results will help determine eligibility for study inclusion (i.e. HbA1c 5.7-6.4%).

Investigators will routinely assess laboratory value excursions for clinical significance.

Adverse events are assessed at every visit once subjects are consented and enrolled to undergo research procedures and study intervention.

6.1.2. Visit 2 (Day --7 to -17 [+/- 2 weeks])+

Eligible subjects will present to the MARC research unit for vital signs, walk distance, grip strength, isometric knee extension strength testing, a body composition DXA scan and liver fibroscan.

6.1.3. Visit 3 (Day -7 to -17 [+/- 2 weeks])

Subjects will come to the Research Imaging Institute for intrahepatic liver fat measurement by Magnetic Resonance Spectroscopy/Imaging.

⁺ Visits 2 and 3 may be performed interchangeably based on DXA and MRI scanner availability.

6.1.4. Visit 4 (Day -1 to -6) -- "Optional"

Participants who opt in will come to the research unit for vital signs and VO2max testing.

Cardiorespiratory fitness is determined by a CPET on an electronically braked cycle ergometer per the American College of Sports Medicine (ACSM) Testing Guidelines. Oxygen consumption and carbon dioxide production are measured by indirect calorimetry. ECG (12-lead) recordings and blood pressure are monitored at rest prior to testing and during the testing. A clinician interprets for contraindications to exercise prior to testing. AHA criteria are used to halt exercise testing [43].

6.1.5. Visit 5 (Day 0)

Eligible subjects present to the research unit fasting at appointed time for a vastus lateralis muscle biopsy (39) and subcutaneous fat biopsy (40). We apply local lidocaine for muscle and adipose biopsies. The muscle biopsy is done using a modified Bergstrom technique with suction and the adipose biopsy is done using a mini-liposuction technique. Urine and blood samples also will be collected. These samples will be used for baseline assays of tissue cellular senescence, DNA methylation, oxidative stress and mitochondrial function. After the muscle and adipose tissue biopsies, subjects will be given breakfast and will receive assignment to treatment intervention (randomized) before being discharged to home. Both treatment and control groups will be given a brochure highlighting healthier eating habits. Subjects in the treatment group will be given a 30-day supply of dapagliflozin to begin use the next day. Subjects in the control group will receive a nutritional consultation with a dietician, which may also be conducted by video telehealth visit, with the goal of losing 3-5% body weight during the 3-month period of the study.

- Once intervention phase begins, the study staff will contact subjects assigned to study drug for telephone follow up at Visit 5 +1 week and at or near midpoint between visits to the research unit up to Visit 8.
- Subjects assigned to nutritional counseling group will receive weekly phone calls/video telehealth visits during the intervention phase which will last for 12 weeks.
- Study team members may contact the subjects by phone at any time for AE follow up as needed.

6.1.6. Visit 6 (Week 4)

Subjects will come to the research unit for evaluation of the biopsy sites and undergo blood draw for CMP to monitor kidney function. Subjects will also have current weight checked at this visit. If necessary, the study coordinator may conduct Visit 6 by home visit and perform the biopsy site check by video telehealth visit. Control group subjects will receive nutritional counseling, which may be performed by home visit or a video telehealth visit.

Drug Refill: Subjects in the treatment group will be given a 30-day supply of dapagliflozin by the Research Drug Manager to begin when their current supply runs out. Study coordinators will ensure treatment compliance by asking subjects to bring drug containers and any remaining dapagliflozin tablets to their visits.

6.1.7. Visit 7 (Week 8)

Subjects in the treatment group will return for T+8 drug refill (in person, by mail, or curbside delivery), and control group subjects will be weighed and receive nutritional counseling, which may be performed by home visit or a video telehealth visit. Control group subjects will receive nutritional counseling, which may be performed by home visit or a video telehealth visit.

6.1.8. Visit 8 (Week 10-11 [+/- 2 weeks])⁺

Subjects will undergo post-treatment measurement of cognition (Montreal Cognitive Assessment), walk

distance, grip strength, isometric knee extension strength, DXA scan and liver fibroscan. Control group subjects will receive nutritional counseling, which may be performed by home visit or a video telehealth visit.

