3.2. General Design

This is a single center, open-label, randomized controlled trial. 20 completed subjects are planned. Each subject will be randomized to either the experimental group of dapagliflozin 10mg daily for 12 weeks or the control group of nutritional counseling for weight loss. Healthspan and clinical evaluations will be taken at baseline and at weeks 10-12 of the study.

Screening data will be reviewed to determine subject eligibility. Subjects who meet all inclusion criteria and none of the exclusion criteria will be entered into the study.

The following treatment regimens will be used:

- Dapagliflozin: 10mg per day for 12 weeks. Subjects will return to refill drug medication and perform compliance check at 4 weeks and 8 weeks after beginning treatment.
- Control Group: Subjects will meet with a dietitian every 1-2 weeks throughout the study to discuss nutritional counseling with a goal to lose 3-5% of body weight over 12 weeks to mirror expected SGLT2

inhibitor-derived weight loss over the same period. During these hour-long sessions, volunteers will learn how to adjust their eating habits by following the recommendations of the American Heart Association for reducing dietary fat and substituting complex carbohydrates and reducing energy intake to induce gradual weight loss while maintaining recommended dietary composition. Volunteers also will receive education on portion sizes, meal timing, and meal preparation. Participants receive a notebook of course content and will weigh in prior to each session. Additional counseling visits and/or phone calls may be instituted if desirable weight loss is not achieved. Subjects may be asked to record their dietary intake for a 24-hour period throughout the intervention for review by the dietitian.

Total duration of subject treatment will be 12 weeks. Total duration of the study is expected to be 16-18 weeks.

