3.3. Study Endpoints

Primary outcome: The primary endpoint for this study is a reduction in urine AGE-RAGE measurements as a result of dapagliflozin treatment. We will be assessing AGE-RAGE in all subjects at baseline and after intervention

Secondary outcomes: Mitochondrial function: This measurement will assess changes in muscle mitochondrial respiration after dapagliflozin treatment. Measurements will occur using muscle samples obtained at baseline and after intervention.

Insulin Sensitivity: This measurement will be obtained before and after the intervention using the HOMA-IR index derived from the fasting insulin and glucose concentrations.

Oxidative Stress: This measurement will be assessed in muscle samples obtained at baseline and after intervention.

Healthspan Measurements: These assessments will include grip strength, isometric knee extension, 6-minute walking distance, and a VO₂Max obtained from CPET. We will be assessing these outcomes in all subjects at baseline and after intervention. Measurements obtained from these exams will evaluate the effect of dapagliflozin treatment on physical indicators of aging.

Cellular Senescence: Senescent cell burden will be assessed in adipose tissue obtained at baseline and after intervention, using both senescence-associated beta-galactosidase staining as well as senescence-associated gene expression assays.

DNA methylation: DNA methylation, a key biological marker of aging, will be evaluated in peripheral blood cells before and after intervention.

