6.1.9. Visit 9 (Week 10-11 [+/- 2 weeks])+

Subjects will return to the Research Imaging Institute to undergo post-treatment Magnetic Resonance Spectroscopy/Imaging for intrahepatic liver fat measurement. Control group subjects will receive nutritional counseling, which may be performed by home visit or a video telehealth visit.

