6.2. Visit Schedule Summary

	VISIT 1	VISIT 2**	VISIT 3**	VISIT 4	VISIT 5	VISIT 6	VISIT 7	VISIT 8***	VISIT 9***	VISIT 10	VISIT 11	VISIT 12
Schedule	-17 days to -21	-7 days to -17, +/- 2wks	-7 days to -17, +/- 2wks	-1 days to -6	Day 0	Week 4	Week 8	Week 10-11, +/- 2wks	Week 10-11, +/- 2wks	Week 11-12	Week 11-12	Week 13
Consent	X											
Vital Signs	Х			Х						Х		
Medical History	Х											
Physical Exam	Х											
MoCA	Х											
Safety Labs (fastin	l ng):											
CBC	Х										Х	
CMP	Х					Х					Х	
Lipid Panel	Х										Х	
PT/PTT/INR	Х											
HbA1c	Х		_	_							Х	
Insulin	Х								_		Х	
FFA	Х										Х	
TSH	Χ											

⁺ Visits 8 and 9 may be performed interchangeably based on DXA and MRI scanner availability.

HSC 20190766H

Version: 2.4 10-29-2020

Routine UA	Х											
DXA		X						Х				
Liver Fibroscan		Х						Х				
MRS/MRI - RII			Х						Х			
Physical Performan	nce:											
Walk Distance		Х						Х				
Grip Strength		Х						Х				
Isom. Knee Ext		Х						Х				
VO2max CPET*				Х						Х		
Muscle Biospy					Х						Х	
SQ Fat Biopsy					Х						Х	
Research Labs:												
Blood					Х						Х	
Urine					Х						Х	
Nutrition consult an	d weight (c	ontrols)			Х	Х	Х					
Nutrition Phone Fol	low Up				weekly	weekly	weekly					
Treatment dispensed				Х	Х	Х						
Treatment Phone F	ollow Up				V5+1w	V6+2w	V7+2w					
Biopsy check						Х						Х
Assess AE		Х	Х	Х	Х	Х	Х	Х	Х	Х	Х	Х

^{*}CPET is optional (Visits 4 & 10)

6.3. Analyses.

Muscle (frozen): Protein oxidative damage will be evaluated from muscle biopsy tissue using immunoblotting against carbonylated protein side chains. DNA from muscle samples will be extracted and tested for 8-hydroxydeoxyguanosine (8-OHdG) content to evaluate oxidative DNA damage and total DNA methylation will be evaluated.

Muscle (fresh): Tissue obtained will be evaluated by an Oroboros Oxygraph-2k high-resolution respirometer to measure mitochondrial respiration capacity. Skeletal muscle fibers will be mechanically separated and permeabilized in BIOPS as described previously to allow uptake of mitochondrial electron transport chain substrates (25). Tissue will then be tested in MiRO6 buffer using a substrate-uncoupler-inhibitor titration (SUIT) protocol to evaluate oxidative phosphorylation capacity.

Fat (frozen): will be subjected to reverse-transcriptase qPCR for measurement of gene expression levels of senescence and SASP markers, including IL-6, TNFα, p16, p21, and MCP1.

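### The two-week tolerance lets the follow-up walk, grip and knee-extension tests fall anywhere from Week 8 to Week 13, against weeks 10-12 in Section 3.2

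*Combined protocol and SAP*

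**What the plan says.** Section 3.2 (General Design) gives the timing as follows: "Healthspan and clinical evaluations will be taken at baseline and at weeks 10-12 of the study". Section 3.3 lists the healthspan outcomes, "These assessments will include grip strength, isometric knee extension, 6-minute walking distance" and VO2max, among the secondary outcomes and adds: "We will be assessing these outcomes in all subjects at baseline and after intervention".

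The visit schedule is wider. Section 6.1.8 is headed "Visit 8 (Week 10-11 [+/- 2 weeks" and opens "Subjects will undergo post-treatment measurement of cognition", followed by the walk, grip, knee-extension, DXA and fibroscan measurements. Section 6.1.9, the liver MRS/MRI visit, is headed "Visit 9 (Week 10-11 [+/- 2 weeks". The Section 6.2 table repeats "Week 10-11, +/- 2wks" for both visits.

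The neighbouring visits have no such tolerance. Visit 7 is at Week 8, when "Subjects in the treatment group will return for T+8 drug refill" (Section 6.1.7). Optional VO2max testing (Visit 10) and the biopsies with blood and urine collection (Visit 11) are both at Week 11-12.

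At baseline, Visits 2 and 3 are set at Day -7 to -17 with the same two-week tolerance. The biopsies and randomisation follow at Visit 5, Day 0.

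**The concern.** A site can follow Section 6.1.8 to the letter and still depart from Section 3.2. At the early end the strength and walk tests coincide with the Week 8 refill visit, with a third of the course still to run. At the late end they fall after the course and possibly after the Visit 11 biopsy. That biopsy is taken from the vastus lateralis, Section 3.4 expects some local bruising after it, and the Study Summary names quadriceps strength as the outcome. At baseline the order is the reverse: knee extension at Visit 2, biopsy at Visit 5.

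Timing matters because the secondary objective (Section 2) is to link biomarker change with change in healthspan, and Section 7.2 does this with within-group Pearson correlations. Section 3.1 plans 20 completers split evenly, so about 10 per arm. The biomarkers come from Visit 11, and the walk, grip and knee-extension results from Visit 8. Variable spacing between the two is an avoidable source of noise in those correlations and in the exploratory group comparisons. Section 7.1 intends the data to guide sample sizes for later studies.

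**Working it through.** **Inputs**
- Treatment course: 12 weeks, or 12 x 7 = 84 days (Section 3.2).
- Visits 8 and 9: Week 10-11, plus or minus 2 weeks (Sections 6.1.8, 6.1.9, 6.2).
- Visits 10 and 11: Week 11-12, no tolerance (Sections 6.1.10, 6.1.11, 6.2).
- Visits 2 and 3: Day -7 to -17, plus or minus 2 weeks; Visit 5: Day 0 (Sections 6.1.2, 6.1.3, 6.1.5).
- Week k is read as k elapsed weeks, Day 7k. Sections 3.2 and 5.2 use weeks this way: the refills they place 4 and 8 weeks after the start are Visits 6 and 7, labelled Week 4 and Week 8.

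**Step 1: reproduce the figure in Section 3.2.** The nominal windows of Visits 8 to 11 run from min(10, 11) = Week 10 to max(11, 12) = Week 12. That is exactly weeks 10-12, so the mismatch comes from the tolerance alone.

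**Step 2: add the tolerance.** 10 - 2 = Week 8 and 11 + 2 = Week 13, so Day 56 to Day 91. The window contains 91 - 56 + 1 = 36 days:
- before weeks 10-12: Day 56 to 69, 14 days;
- within weeks 10-12: Day 70 to 84, 15 days;
- after weeks 10-12: Day 85 to 91, 7 days.

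**Step 3: share of the course elapsed.** At the earliest permitted test, 56/84 = 67%. At the start of the Section 3.2 window, 70/84 = 83%. The latest permitted test is 91 - 84 = 7 days after the course ends.

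**Step 4: spacing from the Visit 11 samples (Day 77 to 84).** Visit 11 day minus Visit 8 day:
- nominal windows (Visit 8 at Day 70 to 77): from 77 - 77 = 0 to 84 - 70 = 14 days;
- with the tolerance (Visit 8 at Day 56 to 91): from 77 - 91 = -14 to 84 - 56 = 28 days.

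The largest lead doubles from 14 to 28 days, and the tests may now follow the samples by up to 14 days. The nominal windows already share Day 77, so the tolerance does not create all of the overlap.

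**Step 5: order relative to the biopsy.** The visit numbers imply that Visit 8 precedes Visit 11, and the named swap pair is Visits 8 and 9 only. No sentence states the order, and the windows do not enforce it.

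**Step 6: baseline window read literally.** -17 - 14 = Day -31 and -7 + 14 = Day +7. Section 5.2 requires screening visits and baseline measurements to be complete before drug is provided at the end of Visit 5, and Section 4.3 makes Visit 2 a screening visit. The positive end is therefore already closed.

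**The case against.** The strongest reply is that Section 3.2 is a design summary giving target weeks and that the schedule adds a working tolerance, which is ordinary drafting. Step 1 supports this, since the nominal windows give weeks 10-12 exactly. The summary of protocol changes shows the wider window was introduced deliberately in version 2.4. This stands as an explanation of how the mismatch arose. It does not remove it: Section 3.2 does not call its weeks nominal, and the two sections still have to be aligned.

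A second reply is that tests and samples were never simultaneous. Nominal baseline testing is already 7 to 17 days before the Visit 5 samples, and the trial is exploratory and not powered. This also stands, and it keeps the point minor. The tolerance nevertheless widens the follow-up gap and allows its direction to reverse.

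A third reply is that separating the performance tests from the scans could mean an extra trip for older participants. That is a fair limit on the remedy. An added trip is a trade-off for the sponsor and is not asked for here.

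The scanner argument must also be kept to what the text says. Sections 6.1 and 6.2 tie only the swapping of visits to scanner availability; the change summary is the only place that connects it with the wider windows. What remains is that walking, grip and knee extension need no scanner and take on the tolerance only by sharing Visit 8 with the DXA.

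**Conclusion.** The point holds as a minor inconsistency with a cheap improvement attached. The schedule permits the walk, grip and knee-extension tests from Day 56 to Day 91, with 21 of the 36 permitted days (14 + 7) outside the Section 3.2 window. The tests may lie from 28 days before to 14 days after the Visit 11 samples. This rests on reading Week k as k elapsed weeks. The documents give no time course for these tests, no effect of a biopsy on strength and no frequency of early or late visits, so the effect on results cannot be derived.

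A reader might infer more than the documents support:
- **Bias between arms.** The window is the same in both arms, and nothing shows that the arms would use it differently.
- **Damage to the main results.** The primary urine AGE-RAGE endpoint and the biopsy outcomes come from Visit 11, and VO2max from Visit 10. Neither visit carries the tolerance.
- **Baseline tests after randomisation.** The literal Day +7 is overruled by Section 5.2 and, for Visit 2, also by Section 4.3. Only the wording needs tidying.
- **A breach of the after-intervention label in Section 3.3.** Nominal Week 10-11 already precedes the end of the 12-week course, so that label is loose whatever the tolerance. The firm conflict is with Section 3.2.
- **A still wider window, by treating Week k as a span of seven days.** The way Sections 3.2 and 5.2 place the refill visits does not fit that reading.

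**What to change.** Reconcile Section 3.2 with Sections 6.1.8, 6.1.9 and 6.2:

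1. State that the follow-up walk, grip and knee-extension tests are done within weeks 10-12 and before the Visit 11 biopsy. If the DXA slot falls outside those weeks, do the tests at another existing visit where possible.
2. Keep the wider tolerance for the DXA and MRI scans, and have Section 3.2 say so, since its sentence also covers clinical evaluations.
3. Record the assessment day for each test, so that the gap to the Visit 11 samples is known at analysis.
4. Wording only: add to the Visit 2 and 3 window that these visits take place before Visit 5.

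If the sponsor does intend Week 8 to Week 13 for the performance tests, Section 3.2 should say that instead. This would remove the inconsistency but leave the variable spacing.

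The cost is a few lines in Sections 3.2, 6.1.2, 6.1.3, 6.1.8, 6.1.9 and the Section 6.2 table, and slightly less scheduling flexibility. No sample size or power figure changes, because the plan states none for power and the target of 20 completers is untouched.
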